#### **10.4.2.** Suspected Adverse Drug Reaction

A suspected adverse drug reaction is any AE for which there is a reasonable possibility that the drug caused the AE. For the purposes of Investigational New Drug safety reporting, "reasonable possibility" means there is evidence to suggest a causal relationship between the drug and the AE. Suspected adverse drug reaction implies a lesser degree of certainty about causality than adverse reaction, which means any AE caused by a drug.

## 10.4.3. Life-Threatening AE or Life-Threatening Suspected Adverse Drug Reaction

An AE or suspected adverse drug reaction is considered "life threatening" if, in the view of either the Investigator or Sponsor, its occurrence places the patient or participant at immediate risk of death. It does not include an AE or suspected adverse reaction that, had it occurred in a more severe form, might have caused death.

## 10.4.4. Serious AE or Serious Suspected Adverse Reaction

An AE or suspected adverse reaction is considered "serious" if, in the view of either the Investigator or Sponsor, it results in any of the following outcomes:

- Death
- A life-threatening AE see definition above
- Inpatient hospitalization or prolongation of existing hospitalization
- A persistent or significant incapacity or substantial disruption of the ability to conduct normal life functions
- Congenital anomaly/birth defect in the offspring of a participant who received study drug

Important medical events that may not result in death, be life-threatening, or require hospitalization may be considered serious when, based upon appropriate medical judgment, they may jeopardize the patient or participant and may require medical or surgical intervention to prevent one of the outcomes listed in this definition. Examples of such medical events include allergic bronchospasm requiring intensive treatment in an emergency room or at home, blood dyscrasias, or convulsions that do not result in inpatient hospitalization, or the development of drug dependency or drug abuse.

#### 10.4.4.1. Serious Adverse Event Definition Clarifications

- Death is an outcome of an AE, and not an AE in itself
- All deaths during study drug administration or up to the follow-up (FU) visit on Day 180, regardless of cause or relationship, must be reported

Page 46 of 65

- "Occurring at any dose" does not imply that the participant is actively receiving study drug at the time of the event
- "Life-threatening" means that the participant was at immediate risk of death from the event as it occurred. This does not include an event that might have led to death, had it occurred with greater severity.
- Complications that occur during hospitalizations are AEs. If an AE prolongs hospitalization, it is a SAE.
- "Inpatient hospitalization" means the participant has been formally admitted to a hospital for medical reasons, for any length of time. This may or may not be overnight. It does not include presentation and care within an emergency department (although an emergency department visit may define a medically important event, which is also considered a SAE).
- The Investigator should attempt to establish a diagnosis of the event based on signs, symptoms, and other clinical information. In such cases, the diagnosis should be documented as the AE or SAE, rather than as the individual signs or symptoms.

## 10.4.5. Unexpected AE or Unexpected Suspected Adverse Drug Reaction

An AE or suspected adverse drug reaction is considered "unexpected" if:

• It is not listed in the Investigator's Brochure or is not listed at the specificity or severity that has been observed

For example, under this definition, hepatic necrosis would be unexpected (by virtue of greater severity) if an Investigator's Brochure referred only to elevated hepatic enzymes or hepatitis. Similarly, cerebral thromboembolism and cerebral vasculitis would be unexpected (by virtue of greater specificity) if an Investigator's Brochure listed only cerebral vascular accidents.

"Unexpected," as used in this definition, also refers to AEs or suspected adverse reactions that are mentioned in the Investigator's Brochure as occurring with a class of drugs or as anticipated from the pharmacological properties of the drug, but are not specifically mentioned as occurring with the particular drug under investigation.

#### 10.5. Adverse Event Classification

## 10.5.1. Relationship to Investigational Drug

The Investigator's assessment of causality must be provided for all AEs (serious and non-serious) (Table 5). An Investigator's causality assessment is the determination of whether there exists a reasonable possibility that the study drug caused or contributed to an AE.

Table 5: Guidelines for Assessing Relationship of Event to Study Drug

Unrelated	There is little or no chance that the Investigational Product caused the AE; other conditions, including concurrent illnesses, progression or expression of the disease state, or a reaction to a concomitant medication best explain the event
Related	The association of the AE with the Investigational Product is unknown, however, the AE is not clearly due to another condition, or a reasonable temporal association exists between the AE and treatment administration and, based on the Investigator's clinical experience, the association of the AE with the Investigational Product seems likely

## **10.5.2.** Severity

All AEs will be graded for severity to describe the maximum intensity of the AE based on Common Terminology Criteria for Adverse Events (CTCAE) (version 5.0) (National Cancer Institute, 2017). For purposes of consistency, these intensity grades are defined in Table 6.

**Table 6:** Guidelines for Severity Assessments

Grade 1	Mild; asymptomatic or mild symptoms; clinical or diagnostic observations only; intervention not indicated	
Grade 2	Moderate; minimal, local or non-invasive intervention indicated; limiting age- appropriate instrumental activities of daily living (e.g., preparing meals, shopping for groceries or clothes, using the telephone, managing money)	
Grade 3	Severe or medically significant but not immediately life-threatening; hospitalization or prolongation of hospitalization indicated; disabling; limiting self-care activities daily living (bathing, dressing and undressing, feeding self, using the toilet, taking medications, and not bedridden)	
Grade 4	Life-threatening consequences; urgent intervention indicated	
Grade 5	Death related to adverse event	

These criteria, in addition to good clinical judgment, should be used as a guide for determining the causal assessment. If the event is believed to be unrelated to study drug administration, then an alternative explanation should be provided.

# **10.6.** Adverse Event Follow-up

All unresolved SAEs ("ongoing" at discharge) will be followed by the study staff until resolution or deemed stable.

# 10.7. Adverse Events of Special Interest

#### 10.7.1. Adverse Events of Noted Interest in IL-10 Protein Trials

Safety will include the following reported IL-10 protein-associated toxicities as defined by CTCAE (v5.0). Systemic levels of XT 150 produced IL-10 protein are expected to be more than 1000-fold lower than when given as a protein solution (Huhn, 1997); and XT-150 will be predominately localized to the facet joint space.

• Grade 1 (unexplained) fever – 38.6°C to 39°C

- Grade 2 allergic, cytokine release, or infusion-related reactions Therapy or infusion interruption indicated but responds promptly to symptomatic treatment (e.g., antihistamines, NSAIDS, narcotics, IV fluids); prophylactic medications indicated for <24 hours
- Grade 2 injection site reaction Pain; lipodystrophy; edema; phlebitis
- Grade 2 neutropenia <1500 to 1000/mm3; <1.5 to 1.0 x109/L

## 10.7.2. Localized Signs of Infection or Inflammation at the Injection Site

Events that, in the opinion of the Investigator, may represent localized signs of infection or inflammation at the XT-150 injection site (e.g., pain, erythema, swelling, pruritus, warmth, hematoma, induration) must be recorded as AEs on the CRF. In general, these events will be temporally related to the injection.

## **10.8.** Toxicity Management

The Investigator should employ best medical judgment in determining how to manage AEs. Any questions regarding AE management should be directed to the Medical Monitor.

#### 11. ASSESSMENT OF EFFICACY PARAMETERS

## 11.1. Efficacy Parameters

Efficacy will be assessed through the evaluation of Visual Analog Scale (VAS) scores, Oswestry Disability Index (ODI) scores, International Physical Activity Questionnaire (IPAQ) scores, SF-12, Participant Global Assessment scores according to the Schedule of Assessments and Procedures in Table 1.

#### 11.1.1. VAS

The VAS will be administered via ePRO at each study visit. The participant will record his/her facet pain level on a scale from 0 (no pain) to 100 (worst pain). Paper questionnaires will be available for completion by the participant as a back-up to the ePRO if needed.

#### 11.1.2. ODI

The ODI captures how a participant's back pain is affecting his/her ability to manage in everyday life. The ODI will be administered via ePRO at each study visit from Baseline through Day 270. Paper questionnaires will be available for completion by the participant as a back-up to the ePRO if needed.

#### 11.1.3. IPAQ

The IPAQ measures physical activity. The IPAQ will be administered via ePRO at each study visit from Baseline through Day 270. Paper questionnaires will be available for completion by the participant as a back-up to the ePRO if needed.

#### 11.1.4. SF-12

The SF12 measures quality of life and functional health and well-being. The SF-12 will be administered via ePRO at each study visit from Baseline through Day 270. Paper questionnaires will be available for completion by the participant as a back-up to the ePRO if needed.

#### 11.1.5. Participant Global Assessment

The Participant Global Assessment asks the participant "Considering all the ways that facet pain, the pain that brought you into this study, affects you, how are you doing today?". The participant answers the question on a scale of 1 to 5, 1 being very good (asymptomatic and no limitation of normal activities) to 5, very poor (very severe, intolerable symptoms and inability to carry out normal activities. The Participant Global Assessment will be administered via ePRO at each study visit from Baseline through Day 270. Paper questionnaires will be available for completion by the participant as a back-up to the ePRO if needed.

## 12. ASSESSMENT OF ANTI-IL-10 ANTIBODIES

Presence of anti-IL-10 antibodies in serum will be assessed. Whole blood for detection of anti-IL-10 antibodies will be drawn at Baseline, then on Days 7, 14, 30, 60, 90, 180, and 270 then processed to serum. Testing will be conducted following completion of the study.

Procedures for collection, storage, and shipping of immunogenicity samples are described in the study Laboratory Manual.

## 13. ASSESSMENT OF XT-150 PLASMID DNA BIODISTRIBUTION

Presence of plasmid DNA in whole blood will be assessed. Whole blood for detection of plasmid DNA will be drawn at Baseline, Day 0 + 4 hours, then on Days 7, 14, and 30. Testing will be conducted following completion of the study.

Procedures for collection, storage, and shipping of plasmid DNA samples are described in the study Laboratory Manual.

#### 14. STATISTICAL METHODS

[figure not shown]
A comprehensive Statistical Analysis Plan (SAP) will be prepared and finalized before database lock. Any changes to the methods described in the final SAP will be described and justified as needed in the clinical study report.

Descriptive statistics (mean, standard deviation, median, minimum, and maximum for continuous variables and count and percentages for categorical variables) for demographics and other baseline characteristics will be provided by treatment group for all participants in the Intent-to-Treat (ITT) and Safety Populations.

# **14.1.** Determination of Sample Size

A total of 72 subjects will be randomized to the 3 treatment groups in a 1:1:1 ratio. As this study occurs early in the clinical development process, the sample size is not based on considerations of statistical power. As an illustration of sensitivity, if a treatment arm shows a responder rate of 50%, the 95% confidence interval around that rate would range approximately from 29% to 71%.

# 14.2. Analysis Populations

The Safety Population will comprise all participants who receive any amount of study drug, analyzed according to treatment actually received.

# 14.3. Analysis of Study Population and Participant Characteristics

Demographics (including age, race, and gender), medical history including history of pain medication use, Baseline assessments (including height, weight, BMI, clinical signs and symptoms, and administration of study drug) will be summarized in the ITT and Safety Populations.

# 14.4. Safety Analysis

All participants who receive any amount of study drug (Safety Population) will be included in the safety analyses.

[figure not shown]
Safety will be evaluated by presenting summaries of AEs, clinical laboratory tests, and vital signs. Safety variables will be tabulated by treatment group.

[figure not shown]
Adverse events will be graded using the CTCAE v5.0 and will be coded using the Medical Dictionary of Regulatory Affairs (MedDRA®), Version 24 or higher. AEs will be collected for each participant from the signing of the informed consent through the last study visit on Day 180.

A treatment-emergent adverse event (TEAE) is defined as an AE that occurs during or after study drug administration. The incidence of TEAEs will be presented by system organ class (SOC) and preferred term (PT), by SOC, PT, and relationship to the study drug administration, and by SOC, PT, and severity. In addition, the incidence of serious TEAEs and TEAEs leading to discontinuation of study drug will be presented by SOC and PT.

Descriptive statistics for clinical laboratory test results, and vital signs, and for changes from Baseline, will be presented by time point. Baseline is defined as the measurement closest to, but prior to, the administration of study drug. Incidences of potentially clinically significant clinical laboratory results, and vital signs, as defined in the SAP, will also be summarized by time point. A summary of abnormal physical examination findings will also be presented.

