#### Table 2:Analysis Populations

Population	Description
All Participants Population	All screened participants who signed the informed consent form. Screen failure information will be summarized using the All Participants Population.
Randomized Population	All participants who met screening criteria and are randomized in the study. This population will be used to determine the other analysis populations
Intent-To-Treat (ITT) Population	All participants who were randomized who received the treatment injection and will be analyzed according to randomized treatment. This population will be used for efficacy.
Safety Population	All participants who received any amount of study drug, analyzed according to their actual treatment received. This population will be used for safety.

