### 8. PROTOCOL VERSION 3.0 ANALYSIS IMPACT

Protocol version 3.0, dated June 8, 2022, made significant changes to the study design including adding a 2nd dose of study drug and two interim analyses. These changes are reflected in the SAP.

Due to this protocol version occurring during the study, some participants will receive only a single injection at baseline and complete the study at day 180 instead of day 270 as per the protocol prior to v3.0 if they did not sign informed consent for v3.0. In effect they will not complete the study under protocol v3.0 and will be considered pre-3.0 participants. These participants will be included in the ITT and Safety populations (if applicable) but will be excluded from the PP population.

Summary tables of the ITT and Safety populations will combine pre-3.0 and post-3.0 participants. Informed consent, disposition, and randomization tables and listings will delineate those who were considered pre-3.0 and those who were post-3.0.

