### **10.4.** Participant Disposition

Participant disposition will be summarized for the Randomized population. Due to this study only having a single dose of treatment at Day 0 and 90, no disposition related to treatment discontinuation is needed in this section as those reasons will be captured in the treatment administration section. Instead, due to protocol v3.0 and the addition of a 2nd dose at day 90, there are four "pathways" that a participant can take in the study and will be summarized from the Day 90 study administration form. Summaries will include:

- Total number of participants who withdrew from study and reason for withdrawal.
- Number of participants who passed day 90 prior to protocol v3.0 reconsent.
  - Number of participants who completed at day 180.
  - Number of participants who discontinued prematurely and reasons for discontinuation.
- Number of participants who were enrolled into protocol v3.0.
  - Number of participants who received the 2nd dose at day 90.
  - Number of participants who completed at day 270.
  - Number of participants who discontinued prematurely and reasons for discontinuation.
- Number of participants who reconsented to protocol v3.0 prior to day 90 to receive a 2nd dose at day 90.

- Number of participants who received the 2nd dose at day 90.
- Number of participants who completed at day 270.
- Number of participants who discontinued prematurely and reasons for discontinuation.
- Number of participants who reconsented to protocol v3.0 prior to day 90 but did not consent to receive a 2nd dose at day 90.
  - Number of participants who completed at day 180.
  - Number of participants who discontinued prematurely and reasons for discontinuation.

A study flow diagram will be produced showing the total number of subjects screened, randomized, treated at day 0 and day 90, and the overall "pathway" of the study including reasons for discontinuation.

Participant disposition data will also be presented in listings.

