### 10.14. Safety Analyses

All safety analyses will be conducted on the safety population. Participants will be summarized by treatment arm, visit (where applicable), and time (where applicable). For all safety analyses, in cases where participants received the wrong study medication, participants will be summarized based on the treatment received.

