#### 10.14.1. Adverse Events

AEs will be coded to system organ class (SOC) and preferred term according to MedDRA, version 24.1. Pretreatment AEs are defined as AEs that have an onset on or after the date the informed consent was signed but before the date of the first dose of study drug. Treatment-emergent adverse events (TEAEs) are defined as AEs that start or worsen after the first dose of study drug. Adverse event severity will be graded using CTCAE v5.0.

Summaries will be provided for TEAEs, with the number and percentage of participants reporting each type of event presented. If a participant reports the same preferred term more than once, it is counted only once within that category. Similarly, if a participant has AEs of two or more preferred terms under the same SOC, then that participant only counts once for that SOC. Furthermore, for a given summary, the preferred term will only be counted once at its worst severity and strongest relationship to study drug.

AEs of special interest will be identified programmatically and reviewed by the study team prior to unblinding. AEs of special interest include:

- (Unexplained) fever
- Grade 2+ allergic, cytokine release, or infusion-related reactions Therapy or infusion interruption indicated but responds promptly to either:
  - symptomatic treatment (e.g., antihistamines, NSAIDS, narcotics, IV fluids)
  - prophylactic medications indicated for  $\leq$ 24 hours
- Grade 2+ injection site reactions
- Grade 2+ neutropenia

The following summaries and listings for AEs will be provided:

- An overall summary table of AEs summarizing the number and percent of participants, in the following categories: any AE, any TEAE, TEAEs by highest severity grade, any TEAEs of special interest, TEAEs by relationship to study drug (related, not related), any serious TEAE, TEAEs leading to drug withdrawal, and TEAEs leading to premature withdrawal from the study, any TEAEs with a fatal outcome
- Incidence of TEAEs by MedDRA SOC and preferred terms
- Incidence of TEAEs by MedDRA SOC, preferred terms, and maximum severity grade
- Incidence of TEAEs by MedDRA SOC, preferred terms, and relationship to study drug.

- Incidence of TEAES of special interest, by SOC, preferred terms, and maximum severity grade.
- Incidence of SAEs by SOC, preferred terms, and maximum severity grade
- Listing of all AEs (with non-treatment-emergent events flagged and AEs of special interest highlighted).
- Listing of all AEs of special interest

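### The percentage of participants with a TEAE leading to drug withdrawal counts people who were never due a second injection, so it understates AE-driven discontinuation of the repeat-dose regimen

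*Protocol*

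**What the plan says.** The primary objective (Protocol 5.1.1, SAP 4.1) is the safety and tolerability of a repeat dose, given on Day 0 and Day 90.

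**Denominator.** Protocol 14.4: "All participants who receive any amount of study drug (Safety Population) will be included in the safety analyses". SAP Table 2 defines the Safety population the same way: "All participants who received any amount of study drug, analyzed according to their actual treatment received. This population will be used for safety". SAP 10.14 allows no exception: "All safety analyses will be conducted on the safety population".

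**Measure.** Protocol 14.4 promises this output: "In addition, the incidence of serious TEAEs and TEAEs leading to discontinuation of study drug will be presented by SOC and PT". In SAP 10.14.1 the overall AE table, which gives number and percent of participants, has a row for "TEAEs leading to drug withdrawal". A listing of these events follows.

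**Pooling.** The second injection came in with protocol v3.0 while the study was running. SAP 8 keeps participants with only the Day 0 injection in the Safety population and adds: "Summary tables of the ITT and Safety populations will combine pre-3.0 and post-3.0 participants". Only the consent, disposition and randomization outputs are split by protocol version.

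**Who was never due dose 2.** The first study pathway in SAP 10.4 is: "Number of participants who passed day 90 prior to protocol v3.0 reconsent". On stopping treatment, the same section says that "no disposition related to treatment discontinuation is needed in this section", because the reasons are to appear under treatment administration (SAP 10.9).

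**The concern.** A participant can stop study drug because of an AE only while some study drug is still to come. Someone already past Day 90 when v3.0 took effect had nothing left to receive once the Day 0 dose was complete. Such people enlarge the denominator and add almost nothing to the numerator.

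The primary objective concerns the repeat dose, and the share of participants who missed the second injection because of an AE bears directly on it. A reader who takes the drug-withdrawal row as that share will find the regimen better tolerated than the data show. If no events occur, the reader will credit the zero with more participants than were ever at risk.

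**Working it through.** **The plan's own figure.** The only computed figure in the documents is in Protocol 14.1: a 50% responder rate in one arm has a 95% interval of about 29% to 71%. The exact (Clopper-Pearson) interval for 12/24 is 29.1% to 70.9%, so this reproduces and confirms n = 24 per arm as the working size. The documents state no rate of discontinuation due to TEAEs.

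**Inputs**
- Arm size 24 (72 randomized 1:1:1, Protocol 14.1), assuming all 24 are dosed.
- m = dosed participants per arm already past Day 90 when v3.0 took effect. Not stated; m = 2, 7 and 12 are assumptions.
- x = participants in the arm whose second injection was not given because of a TEAE. The m participants are assumed to contribute no event, so an incomplete Day 0 dose is set aside.

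**Formulas**
- Planned rate = x/24.
- Rate among those due a second injection = x/(24 - m).
- Planned divided by due = (24 - m)/24, so the relative understatement is m/24.
- With x = 0, the exact two-sided 95% upper limit on n participants is 1 - 0.025^(1/n).

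**Results per arm**

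| m | Number due | (24 - m)/24 | Understatement | Rate among those due if x = 2 (planned: 2/24 = 8.3%) | Upper 95% limit if x = 0 |
|---|---|---|---|---|---|
| 0 | 24 | 1.00 | 0% | 8.3% | 14.2% |
| 2 | 22 | 0.92 | 8% | 9.1% | 15.4% |
| 7 | 17 | 0.71 | 29% | 11.8% | 19.5% |
| 12 | 12 | 0.50 | 50% | 16.7% | 26.5% |

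A further example with m = 8 and x = 3: the planned row shows 3/24 = 12.5%, while the rate among those due is 3/16 = 18.8%.

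The visible SAP plans no interval for AE rates. The last column only shows how much reassurance a zero would carry: with no events, 0/24 seems to exclude rates above 14.2%, but if 12 of the 24 were never due dose 2 the data exclude only rates above 26.5%.

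**The case against.** The strongest reply is that the planned row is the usual summary over all exposed participants, which the protocol requires. Nothing labels it a repeat-dose tolerability rate, and discontinuation due to an AE is not a listed safety endpoint in Protocol 5.2.1 or SAP 4.2. The reply also holds that the relevant figure can largely be recovered from planned outputs: pathway counts in SAP 10.4, reasons for not dosing at each visit in SAP 10.9, and the listing of AEs leading to drug withdrawal. This is a fair reason to keep the all-dosed row, and it limits the harm. It does not correct the printed percentage, because no visible AE output uses participants due a second injection as its denominator.

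A reader might also infer more than the documents support:

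- *That single-injection participants can never have the event.* Each dose is two injections, and Protocol 8.4 and SAP 10.9 both provide for an incomplete dose, so an AE-driven stop on Day 0 is possible.
- *That the SAP drops discontinuation reasons.* SAP 10.4 moves them to SAP 10.9.
- *That the Day 90 percentages in SAP 10.9 are diluted too.* The relevant items there are numbers and reasons; no percentage is stated for them.
- *That about 7 single-dose participants are expected.* The 7 in the SAP efficacy section is a trigger in a sentence that is cut off, not a count.
- *That dilution differs between arms.* Being past Day 90 when v3.0 arrived depends mainly on enrolment date. Under 1:1:1 randomization any imbalance would be mainly chance, and the documents show none.

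Part of the SAP is redacted, including text between sections 8 and 10, so the lack of a visible version-specific AE summary does not prove that none exists. The rule to pool Safety summary tables is visible and explicit.

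**Conclusion.** The point holds for the absolute rate. As planned, the drug-withdrawal percentage is (24 - m)/24 of the rate among participants due a second injection: 8%, 29% or 50% too low for assumed m of 2, 7 or 12. With no events both rates are 0%, and the error lies in how firmly that zero is read. If m is 0 in an arm, nothing is wrong there.

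The size cannot be fixed from the documents because m is not given. The conclusion also rests on all 24 being dosed and on no AE-driven incomplete Day 0 doses among the m. It concerns the level in each arm and makes no claim that the comparison between arms is biased.

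One mismatch is separate and adds nothing to the denominator argument: Protocol 14.4 promises these events by SOC and PT, the visible SAP list has only the overall row and a listing, and SAP 11 does not record the difference.

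This is a low-cost improvement to a potentially misleading percentage.

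**What to change.** In SAP 10.14.1, keep the all-dosed row. Add beside it, by arm and with the denominator printed, the number and percent whose second injection was not given because of a TEAE.

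- **Denominator:** all dosed participants who had not passed Day 90 when v3.0 was implemented. Include those who declined the second dose, those who did not sign the v3.0 reconsent, and those who left the study before Day 90. Show each reason separately.
- **Not by reconsent:** for participants enrolled earlier, reconsent comes after the first dose and may depend on how that dose was tolerated. A denominator limited to those who reconsented could remove the very people who had an AE. The first pathway in SAP 10.4 is worded by reconsent, so the flag should instead compare each participant's Day 90 date, counted from the Day 0 injection, with a stated implementation date.
- **Numerator:** count by the recorded reason for the missed injection, so that someone who declined because of an AE is not lost through AE coding.
- **SAP 10.9:** in the Day 90 part, show participants already past Day 90 as not applicable.

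The cost is SAP wording, one derived flag and one extra row with a different N. The added rate may look less favourable. No new data are needed, and Protocol 14.4 can stand because the all-dosed row remains. SAP 2 provides for an amendment before database lock; after lock, SAP 7.2 would require the row to be labelled post hoc.
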